5.5 Nivolumab administration

Nivolumab is to be administered as an approximate 30-minute IV infusion. For details on prepared drug storage, preparation, and administration, please refer to the Nivolumab Investigator Brochure (IB).

Nivolumab injection is to be administered as an IV infusion through a 0.2-micron to 1.2-micron pore size, low-protein binding polyethersulfone membrane in-line filter at 240 mg. It is not to be administered as an IV push or bolus injection. Nivolumab injection can be infused undiluted (10 mg/mL) or diluted with 0.9% Sodium Chloride Injection, USP or 5% Dextrose Injection, USP to protein concentrations as low as 1 mg/mL. Care must be taken to assure sterility of the prepared solution as the product does not contain any antimicrobial preservative or bacteriostatic agent. At the end of the infusion, flush the line with an adequate amount of normal saline.

5.5.1 DOSE DELAYS FOR NIVOLUMAB (see section 6 for radiation and cisplatin dose modifications and requirements)

**There will be no dose reduction of nivolumab in this protocol.
During Chemo/RT:**

For patients receiving definitive chemoradiation plus nivolumab (cohorts one and three), standard treatment parameters will apply toward administration of weekly cisplatin and/or radiation therapy. **If a dose of cisplatin is held on a treatment week where nivolumab is scheduled, that dose of nivolumab should be skipped and not made up.**

Nivolumab (All Cohorts):

Non-Immune mediated: All toxicities- heme or non-heme- felt to have some causality to nivolumab must resolve to \leq grade 2 (excluding weight loss, weight gain, and alopecia) or to baseline prior to a patient receiving a subsequent dose (of Nivolumab). Any dose of nivolumab not administered will be skipped and not made up.

BrUOG 355: 7/8/17, 7/11/17, 7/20/17, 8/7/17, 8/8/17, 8/14/17, 8/16/17, 8/21/17, 8/22/17, 8/24/17, 8/28/17, 9/5/17, 9/6/17, 9/8/17, 9/11/17, 11/7/17, 11/8/17, 11/19/17 approved DD, 11/20/17, 12/12/17, 12/14/17, 1/29/18, 2/1/18, 2/6/18, 2/7/18, 2/8/18, 2/9/18, 2/12/18, 2/13/18, 3/8/18 all reviews, 3/9/18, 3/13/18, 3/14/18, 3/15/18, 4/19/18, 4/23/18, 5/29/18, 6/5/18, Amendment # 1 7/9/18, Amendment # 2 12/12/18, Amendment #3, 4/6/2020, Amendment #4 5/11/2020

Immune mediated: Adverse events (both serious and non-serious) associated with nivolumab may represent immunologic etiology. Nivolumab must be held for suspected immune-mediated toxicities or severe/life-threatening AEs of particular interest (in Section 7.0) and immune-related toxicities (in Appendix D). Please review both Sections (7 and Appendix D) prior to infusion of nivolumab in any patient in whom immune-mediated toxicity is suspected.

If the investigator is unsure if a particular toxicity at least possibly represents an immune mediated toxicity to nivolumab, the treating physician should follow section 7 and appendix D and treat as immune mediated, until it is confirmed as not being immune mediated. Consultation with BrUOG is suggested in such situations. BrUOG will share information about the situation with the BrUOG Reviewer and PI and provide the site guidance, as available.

Removal from study (all cohorts):

Patients must discontinue nivolumab permanently for the following:

- Any Grade 2 drug-related uveitis or eye pain or blurred vision that does not respond to topical therapy and does not improve to Grade 1 severity within the re-treatment period OR requires systemic treatment
- Grade 3 drug-related thrombocytopenia > 7 days or associated with bleeding
- Any treatment delay resulting in no nivolumab dosing for > 6 weeks.
- Patients who discontinue nivolumab during definitive chemoradiation (cohorts one and three)
- Grade 4 drug-related endocrinopathy adverse events such as adrenal insufficiency, ACTH deficiency, hyper- or hypothyroidism, or glucose intolerance, hypophysitis.
- \geq Grade 4 hepatic AEs
- \geq Grade 4 skin toxicity (per Appendix D can delay or discontinue for grade 3. Must come off, as per this bullet for grade 4 skin)
- ALL OTHER treatment related grade 3/4 treatment related events with the following exceptions:
 - Grade 4 neutropenia \leq 7 days;
 - Grade 4 lymphopenia or leukopenia;
 - isolated Grade 4 electrolyte imbalances/abnormalities that are not associated with clinical sequelae and are corrected with supplementation/appropriate management within 72 hours of their onset;
 - Grade 3 hepatic AEs that return to Grade 2 or less within 5 days Of note, this overrides Appendix D
 - Skin toxicity \leq grade 3 that improves with steroid therapy. NOTE: Any rash consistent with Stevens-Johnson Syndrome or Toxic Epidermal Necrolysis requires permanent discontinuation of nivolumab.
 - Grade 3 renal toxicity (as per Appendix D)

If Nivolumab is discontinued, the patient is to be taken off study. The total treatment patient BrUOG 355: 7/8/17, 7/11/17, 7/20/17, 8/7/17, 8/8/17, 8/14/17, 8/16/17, 8/21/17, 8/22/17, 8/24/17, 8/28/17, 9/5/17, 9/6/17, 9/8/17, 9/11/17, 11/7/17, 11/8/17, 11/19/17 approved DD, 11/20/17, 12/12/17, 12/14/17, 1/29/18, 2/1/18, 2/6/18, 2/7/18, 2/8/18, 2/9/18, 2/12/18, 2/13/18, 3/8/18 all reviews, 3/9/18, 3/13/18, 3/14/18, 3/15/18, 4/19/18, 4/23/18, 5/29/18, 6/5/18, Amendment # 1 7/9/18, Amendment # 2 12/12/18, Amendment #3, 4/6/2020, Amendment #4 5/11/2020

received will be collected, but once patient is off study, all treatment is per standard of care and does not need to follow-BrUOG 355.

In situations when RT is not given (held for toxicity or other reasons (weather, machine is down, holiday), cisplatin and Nivolumab should not be given and should also be held.

If Nivolumab is held on a day Cisplatin is due and the patient meets criteria to receive Cisplatin and Radiation then every attempt should be made to administer Cisplatin and radiation, while holding Nivolumab.

Every attempt should be made for all patients to complete radiation therapy (even if cisplatin and nivolumab are held)

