5.2 ALL PATIENT TREATMENT

5.3 Nivolumab

All patients will receive two doses of nivolumab prior to the start of definitive chemoradiation. During induction and for those receiving concurrent nivolumab with chemoradiation, this study will use a fixed dose of nivolumab 240 mg every 2 weeks during RT, with each 2 week period constituting a cycle. The cycle window will be +/- 3 days (See section 5.5).

BrUOG 355: 7/8/17, 7/11/17, 7/20/17, 8/7/17, 8/8/17, 8/14/17, 8/16/17, 8/21/17, 8/22/17, 8/24/17, 8/28/17, 9/5/17, 9/6/17, 9/8/17, 9/11/17, 11/7/17, 11/8/17, 11/19/17 approved DD, 11/20/17, 12/12/17, 12/14/17, 1/29/18, 2/1/18, 2/6/18, 2/7/18, 2/8/18, 2/9/18, 2/12/18, 2/13/18, 3/8/18 all reviews, 3/9/18, 3/13/18, 3/14/18, 3/15/18, 4/19/18, 4/23/18, 5/29/18, 6/5/18, Amendment # 1 7/9/18, Amendment # 2 12/12/18, Amendment #3, 4/6/2020, Amendment #4 5/11/2020

For patients assigned to maintenance nivolumab (cohorts 2 and 3), nivolumab will be administered at a fixed dose of 480 mg every 4 weeks, with each 4-week period constituting cycle. The cycle window will be +/- 3 days

5.4 COHORT ASSIGNMENT:

All patients will continue on treatment within 14 days (+/- 7 days) following the final dose of nivolumab pre-chemoradiation in one of three cohorts:

Cohorts will be enrolled consecutively with all patients being enrolled to cohort 1 (8 patients) after-which enrollment to cohort 2 will open (to enroll 4 patients). Once safety is confirmed in those cohorts, enrollment to cohort 3 will open and enroll the remaining patients up to a total of 24 evaluable patients.

- Cohort ONE: Nivolumab during chemoradiation (total, 8 patients)
 - o Definitive radiation therapy fields will be determined by the treating radiation oncologist.
 - o Two groups of patients (4/group) will be evaluated dependent on the chemoradiation field, with the field determined and documented in advance by the treating radiation oncologist:
 - COHORT 1A: Patients receiving EFRT +/- HDR/LDR brachytherapy. Parametrial boost is per MD discretion
 - COHORT 1B: Patients receiving WPRT +/- HDR/LDR brachytherapy. Parametrial boost is per MD discretion
 - o Nivolumab 240mg IV every 14 days (+/- 3 days) for 3 doses, administered concomitantly during chemoradiation and beginning day 1 of Radiation. Dosing days of nivolumab will be flexible to align with cisplatin dosing.
 - o Standard cisplatin dosing will be utilized during treatment (40 mg/m² weekly for maximum of 6 doses)

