- Cohort TWO: Chemoradiation followed by Nivolumab maintenance for 2 years (total, four patients)
 - o Patients will proceed with definitive chemoradiation alone.
 - o 2-3 weeks following completion, patients will begin Nivolumab 480 mg IV every 4 weeks (+/- 3 days) for a planned duration of 2 years.
- Cohort THREE: Nivolumab 240mg IV during chemoradiation and then as nivolumab monotherapy 480mg IV (beginning no more than 4 weeks post CRT) for 2 years (total, approximately 12 patients to enroll allow for total study)

BrUOG 355: 7/8/17, 7/11/17, 7/20/17, 8/7/17, 8/8/17, 8/14/17, 8/16/17, 8/21/17, 8/22/17, 8/24/17, 8/28/17, 9/5/17, 9/6/17, 9/8/17, 9/11/17, 11/7/17, 11/8/17, 11/19/17 approved DD, 11/20/17, 12/12/17, 12/14/17, 1/29/18, 2/1/18, 2/6/18, 2/7/18, 2/8/18, 2/9/18, 2/12/18, 2/13/18, 3/8/18 all reviews, 3/9/18, 3/13/18, 3/14/18, 3/15/18, 4/19/18, 4/23/18, 5/29/18, 6/5/18, Amendment # 1 7/9/18, Amendment # 2 12/12/18, Amendment #3, 4/6/2020, Amendment #4 5/11/2020

enrollment of up to total 24 patients on study)

- Patients will receive nivolumab during definitive chemoradiation (as in cohort one) followed by nivolumab alone (as in cohort two). Pending safety data of cohort one, patients may be stratified by the radiation field, as in cohort One.

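### The six-week nivolumab removal rule has no stated starting point, so one skipped 4-weekly maintenance dose either takes the patient off study or does not, depending on how the site counts

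*Combined protocol and SAP*

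**What the plan says.** Section 5.5.1 lists the reasons for which nivolumab must be stopped for good, under a subheading that covers all cohorts. One of them is "Any treatment delay resulting in no nivolumab dosing for > 6 weeks". The section then adds: "If Nivolumab is discontinued, the patient is to be taken off study".

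The same section allows no dose reduction. Non-immune toxicity attributed to nivolumab must settle to a stated grade or to baseline before the next dose, and "Any dose of nivolumab not administered will be skipped and not made up". The removal list carries exceptions, among them grade 3 hepatic events that settle within 5 days and skin toxicity up to grade 3 that improves on steroids. It also notes that Appendix D permits either delay or discontinuation for grade 3 skin toxicity. Section 7.1.1 refers to a treatment delay under Appendix D for grade 2 diarrhea or colitis.

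On the schedule, section 5.3 says "All patients will receive two doses of nivolumab prior to the start of definitive chemoradiation", and section 5.4 says "All patients will continue on treatment within 14 days (+/- 7 days) following the final dose of nivolumab pre-chemoradiation". For cohort 2, "Patients will proceed with definitive chemoradiation alone", and then "2-3 weeks following completion, patients will begin Nivolumab 480 mg IV every 4 weeks". Cohort 3 receives nivolumab every 14 days for three doses from day 1 of radiation, and starts 4-weekly maintenance no more than 4 weeks after chemoradiation.

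The term treatment delay is not defined. Nothing says whether the six weeks run from the last dose given or from the date the missed dose was due, and no separate limit is given for 4-weekly dosing.

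**The concern.** The limit is one number applied to two dosing intervals. On the 2-weekly schedule it leaves room for a missed dose. On the 4-weekly schedule, counted from the last dose, it leaves room for none, because a skipped dose may not be made up and the next one falls about eight weeks after the last. The text that holds a dose until toxicity resolves, the exceptions to discontinuation and the option to delay all suppose that a patient can miss a dose and continue. In maintenance, that count takes the possibility away.

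Two sites could therefore handle the same patient in opposite ways, both within the text. What is at stake is how much maintenance nivolumab patients receive, and who contributes toxicity data from a maintenance period of up to two years in cohorts of four and about twelve.

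**Working it through.** The documents state no dose-free interval, so there is no figure to reproduce. The check is calendar arithmetic against 6 × 7 = 42 days.

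**Inputs**
- Maintenance interval 28 days, window ± 3 days (5.3, 5.4).
- Last induction dose to start of chemoradiation: 14 ± 7 days, so 7 to 21 (5.4).
- Chemoradiation: about 6 weeks (5.6), taken as ending on day 42. Shortest case: 25 external-beam fractions at five a week from a Monday, ending on day 33. Longest: day 60 (5.7). Section 5.7.5 instead requires completion within 6 weeks; these two passages disagree.
- Completion to first maintenance dose: 14 to 21 days in cohort 2; at most 28 days in cohort 3 (5.4). Cohort 3 has no stated minimum, so 14 days is assumed from cohort 2.
- Concurrent doses on days 1, 15 and 29 (5.4), nominal dates.

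**One skipped maintenance dose**
- From the last dose given: 2 × 28 = 56 days; with ± 3 days at each end, 50 to 62. Always above 42.
- From the missed due date: 28 ± 3 = 25 to 31 days. Never above 42.
- No skip: 28 ± 6 = 22 to 34 days.

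**2-weekly dosing, for comparison**
- One skip: 2 × 14 = 28 days, 22 to 34 with windows. Below 42 on either count.
- Two consecutive skips: 3 × 14 = 42 days, which is not more than 42 on nominal dates.

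**Cohort 3, last concurrent dose to first maintenance dose**
- No skip, radiation ending by day 42: at most (42 − 29) + 28 = 41 days. Below the limit.
- No skip, radiation ending on day 60: (60 − 29) + 14 = 45 to (60 − 29) + 28 = 59 days. Above it.
- Day-29 dose skipped, for example because cisplatin was held, radiation ending on day 42: (42 − 15) + 14 = 41 to (42 − 15) + 28 = 55 days. Can exceed it.

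**Cohort 2, last induction dose to first maintenance dose**
- Six-week course: 14 + 41 + 14 = 69 to 14 + 41 + 21 = 76 days (9.9 to 10.9 weeks).
- Shortest: 7 + 32 + 14 = 53 days. Longest: 21 + 59 + 21 = 101 days.
- Every scheduled path exceeds 42 days.

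**The case against.** A reader might infer that every cohort 2 patient meets the removal rule simply by following the schedule, and that schedule and rule cannot both be followed. The documents do not support this. The trigger is a delay, in a section about dose delays, and a planned break is not one. Section 7.2 speaks of delays due to adverse events as against treatment continuing as each cohort indicates. Another item in the removal list, on stopping nivolumab during chemoradiation, names only cohorts one and three, so the list recognizes that cohort 2 receives none then. Section 16.1.1 places cohort 2's safety evaluation 4 weeks into maintenance, so these patients are expected to get there. That much of the objection stands. What remains for cohort 2 is that the exemption is left to inference under a rule addressed to all cohorts.

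The objection also runs that a skipped dose creates no contradiction: a ban on making up a dose promises no later dose, so one skip followed by discontinuation is strict but can be carried out, and a count from the due date avoids the problem. It can be carried out, but it defeats the hold-and-resume provisions in maintenance. The words about no nivolumab dosing for more than six weeks favor the last-dose count without settling it. The skip sentence also stands in the paragraph on non-immune toxicity, although it is worded for any dose; if a late dose were allowed after an immune-related hold, it could slip 42 − 28 = 14 days before the last-dose count reached the limit. That adds to the ambiguity.

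Finally, removal from nivolumab is not a feasibility criterion. Section 16.1.1 uses persistent grade 3 or higher events and completion of chemoradiation within 8 weeks. Cohort 2's review comes too early for a skipped maintenance dose to have produced a six-week gap, and section 16.2 keeps everyone who starts therapy in the toxicity evaluation until 30 days after last treatment unless the patient withdraws. This stands, and limits the consequence.

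**Conclusion.** The point holds for skipped maintenance doses. On the last-dose count a single skip gives 56 days (50 to 62) and requires permanent discontinuation, against the text that provides for holding and resuming; on the due-date count it gives 25 to 31 days and does not. The plan does not choose between them.

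It holds conditionally for cohort 3. The 45 to 59 days need radiation to run to day 60, as section 5.7 allows and section 5.7.5 does not, and maintenance to start 2 to 4 weeks later. The upper figure of 55 days within a six-week course needs the day-29 dose to be skipped. With no skip and radiation finished by day 42, the limit is not exceeded.

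For cohort 2 the finding is only that a planned break of 53 to 101 days is not expressly exempted.

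Up to 4 + 12 = 16 patients enter maintenance. The documents give no rate of skipped doses, so the number who would be removed cannot be calculated. The effect falls on maintenance exposure and the maintenance toxicity data, since reporting of all adverse events ends 30 days after last treatment (8.5). The rules for opening the next cohort are not affected.

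**What to change.** Reconcile section 5.5.1 with sections 5.3 and 5.4 and with the skip rule. The text should state:
- what counts as a treatment delay;
- from which dose or date the six weeks run in induction, during chemoradiation, at the move to maintenance, and in maintenance;
- whether a single skipped 4-weekly dose counts;
- how the planned gaps in cohorts 2 and 3 are treated, in explicit words;
- how the rule fits with the hold-until-resolved text, the listed exceptions and the Appendix D delay option.

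The radiation completion times in sections 5.7 and 5.7.5 should be reconciled at the same time, because the cohort 3 interval depends on them. Which limit applies, and in which phase, is the sponsor's clinical decision.

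In the analysis, report by cohort the number of patients removed under this rule, with the interval observed and the dose from which it was counted. The cost is a few sentences in a protocol amendment and one line in a disposition table; it needs no new data beyond dosing dates and reason for removal.

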Pelvic Tumor Volume (PTV)	Required dose = 45 Gy	Around CTV1, a 15 mm uniform expansion should be used. Around CTV2, a 10 mm uniform expansion should be used. Around CTV3 (and CTV_boost, if applicable), a 5 mm uniform expansion should be used. These expansions will generate PTV1, PTV2, and PTV3, respectively. PTV1-3 will be fused to generate the PTV .
PTV-skin	IF applicable only: PTV-3mm from skin surface	The PTV should be manually or automatically trimmed up to 3 mm from the skin surface, if necessary, to spare skin. However, the CTV still needs to be included entirely within the PTV .
PTV-boost	Required dose = 54 to 59.4 Gy	5 mm uniform expansion around CTV_Boost

Brachytherapy (point-directed)

The definition of all points (A, B, Bladder, Rectum and Vaginal Surface) will be in accordance with the 1985 ICRU Report #38: Dose and Volume Specifications for Reporting Intracavitary Therapy in Gynecology.

BrUOG 355: 7/8/17, 7/11/17, 7/20/17, 8/7/17, 8/8/17, 8/14/17, 8/16/17, 8/21/17, 8/22/17, 8/24/17, 8/28/17, 9/5/17, 9/6/17, 9/8/17, 9/11/17, 11/7/17, 11/8/17, 11/19/17 approved DD, 11/20/17, 12/12/17, 12/14/17, 1/29/18, 2/1/18, 2/6/18, 2/7/18, 2/8/18, 2/9/18, 2/12/18, 2/13/18, 3/8/18 all reviews, 3/9/18, 3/13/18, 3/14/18, 3/15/18, 4/19/18, 4/23/18, 5/29/18, 6/5/18, Amendment # 1 7/9/18, Amendment # 2 12/12/18, Amendment #3, 4/6/2020, Amendment #4 5/11/2020

Brachytherapy (volume-directed)

The MRI based target delineation can be reused by superimposition in the process of contouring on CT, if for subsequent fractions of brachytherapy only CT can be used with the applicator in place. No planning margins will be added to the CTV.

Standard name	Description	Specification
GTV	Required dose = 27.5-30 Gy	Macroscopic tumor (if present) at time of brachytherapy
CTV		GTV + whole cervix + presumed extra cervical tumor extension

Compliance criteria:

	Per protocol	Variation (Acceptable)	Deviation (Unacceptable)*
Overall Treatment time	≤ 60 days	≤ 66 days	>66 days

Patients who require a treatment delay of RT for 7 consecutive days or longer will be removed from this protocol. The decision to continue standard chemoradiation will be left to the treating physician. See Section 6.2.

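### As worded, the 6-week nivolumab stopping rule can take a cohort 3 patient off study who misses the third concurrent dose and starts maintenance on time

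*Combined protocol and SAP*

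**What the plan says.** - **Stopping rule.** Section 5.5.1 (removal from study, all cohorts) lists among the reasons for permanent discontinuation "Any treatment delay resulting in no nivolumab dosing for > 6 weeks". A patient who discontinues nivolumab is taken off study. The term for the triggering delay is not defined, and no exemption is given for the step from chemoradiation to maintenance.
- **Concurrent dosing.** Section 5.4 gives cohort 1 "Nivolumab 240mg IV every 14 days (+/- 3 days) for 3 doses", starting on the first day of radiation. Cohort 3 follows the same schedule.
- **Maintenance start.** For cohort 3, Section 5.4 specifies "nivolumab monotherapy 480mg IV (beginning no more than 4 weeks post CRT) for 2 years", and it also refers to cohort 2 for the maintenance phase. Cohort 2's wording is "2-3 weeks following completion, patients will begin Nivolumab 480 mg IV every 4 weeks".
- **Missed doses.** Section 5.5.1 says "Any dose of nivolumab not administered will be skipped and not made up". The same applies to a nivolumab dose due in a week when cisplatin is held. When radiation is not given, "cisplatin and Nivolumab should not be given and should also be held".
- **Radiation holds.** Section 5.7.3 says "Patients who require a treatment delay of RT for 7 consecutive days or longer will be removed from this protocol". A hold of six days or less therefore leaves the patient on protocol.
- **Replacement.** Section 16.2 replaces only patients who withdraw before finishing the third week of chemoradiation.

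**The concern.** Two clocks cover the same interval from different starting points. The stopping rule counts from the last nivolumab dose; the maintenance window counts from the end of chemoradiation. When the third concurrent dose is missed, the first clock starts two weeks earlier and the second does not move. A patient can then satisfy Section 5.4 and still meet a removal criterion in Section 5.5.1. Nothing in Sections 5.4, 5.5.1 or 7.2 reconciles them.

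The trigger is ordinary. The third dose is due on day 29, which is also a cisplatin day (Section 5.6). Section 6.1 gives several routine reasons to hold cisplatin: neutrophils, platelets, creatinine, gastrointestinal toxicity.

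Cohort 3, about 12 patients, is the only cohort given both concurrent and maintenance nivolumab. Each patient removed is about 8% of it (1/12), loses up to two years of planned maintenance, and is past the point at which Section 16.2 allows replacement. Section 16.1 counts events during maintenance in the primary toxicity endpoint, and Section 16.1.1 plans a cohort 3 safety analysis after maintenance. Both depend on who starts it.

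**Working it through.** The plan gives no figure of its own to reproduce; this is calendar arithmetic.

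**Inputs**
- Limit: 6 weeks = 42 days (5.5.1).
- Concurrent doses on radiation days 1, 15 and 29, each ±3 days (5.4). Nominal days are used below.
- D = day radiation ends. Section 5.6 says about six weeks, so D = 40 and D = 42 are assumptions. D = 48 adds one 6-day hold to day 42. It is inside the 60-day limit of Section 5.7 but beyond the 6-week limit of Section 5.7.5.
- L = day of last nivolumab: 29 if all doses are given, 15 if dose 3 is skipped.
- s = days from the end of radiation to first maintenance: up to 28, or 14 to 21 if the cross-reference to cohort 2 fixes the timing (5.4).

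**Formulas.** Gap = D + s − L. The rule is breached when the gap exceeds 42. The latest start that fits is s = 42 − (D − L).

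| Case | D | L | Gap, s = 14 | Gap, s = 21 | Gap, s = 28 | Latest s that fits |
|---|---|---|---|---|---|---|
| Dose 3 skipped | 40 | 15 | 39 | 46 | 53 | 17 |
| Dose 3 skipped | 42 | 15 | 41 | 48 | 55 | 15 |
| Dose 3 skipped | 48 | 15 | 47 | 54 | 61 | 9 |
| All given | 40 | 29 | 25 | 32 | 39 | 31 |
| All given | 42 | 29 | 27 | 34 | 41 | 29 |
| All given | 48 | 29 | 33 | 40 | 47 | 23 |

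**Reading the table**
- On schedule, the latest allowed start fits (41 days with D = 42).
- With dose 3 skipped and no lengthening of radiation, starts after day 15 (D = 42) or day 17 (D = 40) breach. That is most of the four-week window and part of the two-to-three-week window.
- With dose 3 skipped and D = 48, the whole two-to-three-week window breaches.
- With all doses given and D = 48, only starts on days 24 to 28 breach, so this case depends on the four-week window governing.

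**Comparison with cohort 2.** From the second induction dose to maintenance, the planned gap is 14 days to radiation, plus 41 (day 1 to day 42), plus 14 to 21: 69 to 76 days.

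**Whether a skipped dose is a delay.** The skip rules sit in Section 5.5.1, which is headed as dealing with nivolumab dose delays. Section 5.7.3 uses the delay term for a radiation hold. Section 7.1.2 describes cisplatin as delayed and then has the nivolumab dose skipped. On that vocabulary, a gap beyond 42 days that follows a cisplatin or radiation hold falls within the rule's ordinary wording.

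**The case against.** The strongest reply is that the rule means lateness of a dose that is due. Cohort 2's planned gap of 69 to 76 days shows that a raw count between doses cannot be intended, and a cohort 3 patient who starts inside the Section 5.4 window has no late maintenance dose. Part of this stands. A reader might infer that the rule removes every cohort 2 patient by design. The documents do not support that, because a planned interval is not a delay. A site could also decide that a skipped dose is not a delay. But the plan never says so, and its own usage points the other way.

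Second, cohort 3 has a stated maximum and no explicit minimum, so starting early can satisfy both rules. A reader might infer that the two rules are irreconcilable. In general they are not: with dose 3 skipped, a start by day 15 fits when D = 42 and by day 9 when D = 48. The exception is the two-to-three-week reading with D = 48, where no start fits. Nothing tells sites to start early for this reason.

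Third, the inference that any short radiation hold causes removal is too strong. With all doses given, the breach is confined to late starts. A short hold need not cost dose 3 either: Section 5.4 allows ±3 days and flexible alignment with cisplatin, and Section 5.6 moves doses to the next working day after closures and holidays. These limits stand.

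Fourth, toxicity data are not lost. Everyone who begins therapy is counted up to 30 days after the last treatment, unless they withdraw (16.2), and central registration and monitoring (Sections 4 and 14.7) may keep sites consistent. That is fair. What is lost is maintenance exposure in the one cohort designed to study it.

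**Conclusion.** The point holds for one main case and should be fixed. In cohort 3, when the third concurrent dose is skipped because cisplatin or radiation is held, the ordinary wording of Section 5.5.1 takes off study patients who start maintenance within Section 5.4. The gap is 48 or 55 days at a 21- or 28-day start with radiation ending on day 42, and 46 or 53 days if it ends on day 40. Only starts by about day 15 to 17 after radiation escape. The all-doses-given case is minor.

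This rests on nominal dosing days, on an assumed radiation end of day 40 to 42, on a hold lengthening radiation day for day, and on reading a skip that follows a hold as a treatment delay. The plan gives no skip or hold rate, so the number of patients affected cannot be estimated. Confidence is medium, because the wording admits a looser reading. The plan accepts a gap of about 69 to 76 days at the same step in cohort 2, so the 42-day cap has no evident purpose in cohort 3 when the missed dose had nothing to do with nivolumab toxicity.

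**What to change.** Add to the 6-week bullet in Section 5.5.1:

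*This rule does not apply to the interval between the last nivolumab dose before or during chemoradiation and the first maintenance dose (cohorts 2 and 3), which must instead start within the 5.4 window after completion of chemoradiation, including brachytherapy; if a dose was held for suspected nivolumab-related toxicity, the 6 weeks still run from the last dose given.*

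Leave unchanged the requirement that toxicity resolve before the next dose, the rule on discontinuing nivolumab during chemoradiation, and the other stopping criteria in Section 5.5.1. The Section 5.4 windows also stay as they are.

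The cost is one sentence in an amendment, with no new visits or data. The downside is that some cohort 3 patients resume nivolumab after a longer gap: with dose 3 skipped, radiation to day 60 and a 28-day start, 60 + 28 − 15 = 73 days, similar to cohort 2's plan.

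The clinical team should settle two details. If doses 2 and 3 are both skipped (last dose day 1), the same dates give 60 + 28 − 1 = 87 days; the team should say whether that counts as discontinuing nivolumab during chemoradiation. In cohort 2, the toxicity clause would stop any patient whose second induction dose was held for suspected nivolumab toxicity, because the planned gap alone exceeds 42 days; the team should confirm that this is wanted.

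### Section 5.5.1: three exceptions to the permanent nivolumab stop name grade 4 only, so as written the milder grade 3 form takes the patient off study and the grade 4 form does not

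*Combined protocol and SAP*

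**What the plan says.** The part of section 5.5.1 on removal from study (all cohorts) lists events for which nivolumab must be permanently discontinued. After the itemised bullets comes a catch-all: "ALL OTHER treatment related grade 3/4 treatment related events with the following exceptions". It has six exceptions.

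- Three name grade 4 alone: "Grade 4 neutropenia" lasting 7 days or less; "Grade 4 lymphopenia or leukopenia", with no time limit; and "isolated Grade 4 electrolyte imbalances/abnormalities that are not associated with clinical sequelae and are corrected with supplementation/appropriate management within 72 hours" of onset.
- Three name grade 3: "Grade 3 hepatic AEs that return to Grade 2 or less within 5 days"; skin toxicity up to "grade 3 that improves with steroid therapy"; and grade 3 renal toxicity as per Appendix D.

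The text after the list says that a patient whose nivolumab is discontinued is taken off study.

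Higher up in 5.5.1, the rule for non-immune toxicity in all cohorts reads: "All toxicities- heme or non-heme- felt to have some causality to nivolumab must resolve to" grade 2 or less, or baseline, before the next dose. Missed doses are skipped.

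**The concern.** An exception should spare an event and its milder forms. Here three exceptions spare the severe form and leave the milder one under the stop. A patient with grade 4 lymphopenia may continue, and a patient with grade 3 lymphopenia may not. A patient with grade 4 neutropenia for six days may continue, and a patient with grade 3 neutropenia for one day may not.

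A site that follows the text must end protocol nivolumab for an event milder than one the protocol tolerates. A site that follows the apparent intent will hold and resume. With 8, 4 and about 12 patients per cohort, sites should not have to choose between these. At least one of the event types is foreseen: section 7.1.3 describes low calcium with low magnesium and potassium as common, and replacement as usually effective.

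**Working it through.** The plan states no figure on this point, so there is none to reproduce. The check applies the rule literally and then counts the nivolumab doses at stake.

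**Step 1. The rule as written.** A treatment-related grade 3 or 4 event stops nivolumab unless an exception matches. Neutropenia, lymphopenia/leukopenia and electrolyte events have no itemised bullet of their own, so the catch-all reaches them however its opening words are read.

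| Event | Grade 3 | Grade 4, exception met | Grade 4, exception not met |
|---|---|---|---|
| Neutropenia | stop, any duration | no stop (7 days or less) | stop (over 7 days) |
| Lymphopenia/leukopenia | stop | no stop | not applicable (no condition) |
| Electrolytes | stop, even if corrected in 72 hours | no stop (isolated, no sequelae, corrected in 72 hours) | stop |

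The inversion appears in all three rows. The firm count is 3 of the 6 exceptions.

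**Step 2. Does other text cure it?**

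- The 5.5.1 re-dosing rule covers haematological toxicity and lets dosing resume after recovery. It sets a condition for the next dose and adds no exception to the stop list.
- Section 6.1 withholds cisplatin below an ANC of 1,000/mcl. Section 5.5.1 then skips a nivolumab dose scheduled for that week. That is a hold.
- Section 6.2 treats neutropenia below grade 4 as uncomplicated and continues radiation. After recovery from complicated toxicity, radiation restarts even if nivolumab is held. The word is held, not stopped.

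All three point to hold and resume. None amends the list.

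**Step 3. Planned nivolumab doses** (sections 5.3 and 5.4).

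- Induction: 2. Concurrent with chemoradiation: 3. Maintenance, 2 years every 4 weeks: 104/4 = about 26.
- Cohort 1: 2 + 3 = 5. Cohort 2: 2 + 26 = 28. Cohort 3: 2 + 3 + 26 = 31.

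**Step 4. Largest loss from a cisplatin-related event.** In cohorts 1 and 3, concurrent nivolumab starts on day 1 of radiation (5.4). Cisplatin starts the same day, and nivolumab is infused first (5.6). Unless that dose is skipped, 2 + 1 = 3 doses have been given before any cisplatin effect. In cohort 2 only the 2 induction doses have been given.

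- Cohort 1: (5 − 3)/5 = 2/5 = 40%.
- Cohort 2: (28 − 2)/28 = 26/28 = 93%.
- Cohort 3: (31 − 3)/31 = 28/31 = 90%.

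A later event costs less. In cohort 1 it is 1/5 = 20% after the fourth dose and 0/5 after the fifth. In cohort 3 it is 26/31 = 84% after the fifth dose.

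**The case against.** The best defence is that no sensible site would apply the text this way. The operating rules in 5.5.1, 6.1 and 6.2 tell it to hold and continue. A grade 4 neutropenia normally passes through grade 3 as it recovers, so the literal reading would defeat its own exception. This is good evidence of intent. It does not alter a list headed by a mandatory stop. Nor can grade 4 be taken to include lower grades, because the skin exception is written as grade 3 or below and the hepatic and renal exceptions name grade 3.

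The second defence concerns frequency, and it largely stands. The cisplatin route needs the catch-all's relatedness to cover cisplatin and radiation, as study treatment does in the reporting text of section 8.7. Section 5.5.1 is a nivolumab section, and several neighbouring bullets refer to drug-related events. If the catch-all means nivolumab only, the lists in section 8.1, which are not complete, name none of the three event types. Section 7.1.3 gives neither a grade nor a rate.

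A reader might infer more in three places, and the documents do not support it.

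- **Larger losses.** Removal straight after induction would forgo 3/5 (60%) in cohort 1 and 29/31 (94%) in cohort 3. A cisplatin-related event cannot produce these figures unless the third dose is skipped, because that dose precedes the first cisplatin.
- **A fourth event type.** One bullet limits the stop to "Grade 3 drug-related thrombocytopenia > 7 days or associated with bleeding". If the catch-all also reaches other grades and durations of itemised types, as the hepatic and skin exceptions suggest, that limit has no effect. But the same reading catches grade 3 endocrinopathy, whose bullet names grade 4. The count is therefore 3 on the narrow reading and at least 5 on the broad one, never 4. Only the 3 are firm.
- **Damage to the feasibility decision.** Neither criterion in 16.1.1 counts nivolumab discontinuation. Treated patients stay in the toxicity evaluation unless they withdraw (16.2), and those removed for toxicity are followed unless they withdraw consent for follow-up (7.3).

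**Conclusion.** The concern holds as an error in a stated rule. For three event types, section 5.5.1 as written removes the patient with the grade 3 event and keeps the patient with the grade 4 event, and no other section corrects this. It is most likely a drafting slip.

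The consequence is lost nivolumab exposure, not a changed endpoint or threshold. The upper limits for a cisplatin-related event are 40% of planned doses in cohort 1, about 93% in cohort 2 and about 90% in cohort 3. They assume no skipped dose, about 26 maintenance doses and a catch-all that includes cisplatin-related events. The number of patients affected cannot be derived, because the documents give no rate for these grade 3 events.

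**What to change.** In the three exceptions, replace grade 4 with grade 3 or 4. Keep the 7-day limit for neutropenia, and keep the isolated, no-sequelae and 72-hour conditions for electrolytes. Leave the rest of the catch-all in force. Grade 3 and grade 4 then get the same answer in every row of the table. The re-dosing rule still requires recovery of nivolumab-related toxicity to grade 2 or less, or to baseline, before the next dose.

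Four matters go beyond removing the inversion and are for the investigators to decide:

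- whether grade 3 neutropenia lasting over 7 days should be excepted;
- whether grade 3 thrombocytopenia of 7 days or less without bleeding should be excepted;
- whether grade 3 endocrinopathy should be excepted;
- whether relatedness in the catch-all means nivolumab only.

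The cost is three lines of text. Because they change a stopping rule, they need a protocol amendment with BMS and IRB approval (sections 13.2, 13.3 and 14.3). No data collection, sample size or feasibility threshold changes.
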